9.0 Procedures Involved

9.1 *Describe and explain the study design.*

This pilot study will include 52 lung cancer survivors using a 2X2 mixed model with Pre-Post assessments in two groups. Twenty-six participants will be randomized to red yellow directed light (control) and 26 participants will receive blue green (experimental) directed light therapy. The light source (Re-Timer) will be worn for 60-minutes every morning within 30-minutes upon awakening for 1-week. Participants will receive a weekly telephone call to ensure adherence to treatment plan and screen for safety/adverse events.

9.2 *Provide a description of all research procedures being performed and when they are performed, including procedures being performed to monitor subjects for safety or minimize risks.*

Screening for inclusion criteria includes a YES response to the following questions:

Are at least 21 years of age?

Do you have a diagnosis of non-small cell lung cancer stage I, II or III?

Have you had your lung cancer surgically removed at least 6 weeks ago, but not longer than 3 years ago?

Screening for exclusion criteria includes a NO response to the following questions:

Do you have any unmanaged medical or psychiatric diagnoses?

Are you currently pregnant?

Do you have a diagnosis of epilepsy?

Following informed consent, in order to rule-out sleep apnea as a confounder and assess for respiratory disturbance, all eligible participants will be screened for sleep apnea and hypoxia using the portable ApneaLink device for one night. Following a negative screen for sleep apnea, demographics, diagnoses, treatments, comorbidities, etc. will be recorded using the Demographics and Treatment Survey. Fatigue will be measured using the Functional Assessment of Chronic Illness Therapy Fatigue (FACIT) (Cella, Lai et al. 2011). Sleep continuity disturbance will be determined by Insomnia Severity Index (Bastien et al., 2001), 14-day sleep diary and the Epworth Sleepiness Scale (Johns 1991). Circadian activity rhythm disturbance will be assessed using the 14-day actigraph (Ambulatory Monitoring, Inc, Ardsley, NY) and Morningness-Eveningness Horne-Ostberg/Questionnaire (MEQ) (Horne and Ostberg 1976). Surveys and actigraphy will be performed at baseline and again after treatment ends. Expectation for treatment effectiveness will be assessed with the investigator developed Expectation Questionnaire before and

after treatment. Treatment adherence and safety will be evaluated by self-report start/end time on sleep diaries and with weekly telephone/text reminders.

9.3 Describe procedures performed to lessen the probability or magnitude of risks.

Weekly telephone calls will be negotiated and utilized to identify Adverse Events and adherence, in addition to self-report adherence on sleep diaries.

9.4 Describe all drugs and devices used in the research and the purpose of their use, and their regulatory approval status.

Response:

- **Direct Light Therapy** - Re-Timer is a directed light device, worn like a pair of glasses that produces a 100% UV-free red-yellow (dim light-control) or blue-green (bright light-experimental), which may improve sleep and reset circadian rhythms. Regulatory status: classified as a wellness device (no FDA classification as medical device)
- **ApneaLink** – ApneaLink is a compact, lightweight, portable device used for overnight screening for sleep apnea, providing information about respiratory effort, pulse, oxygen saturation, nasal flow and snoring. Regulatory status: approved (FDA)
- **Actigraphy (Ambulatory Monitoring, Inc., Ardsley, NY)** – is a wrist worn device that uses a piezoelectric sensor that generates a signal based on movement. The analog signal is then digitalized and for each 1-minute epoch an activity count is calculated and stored. Software application allow for objective sleep-wake patterns (total sleep time, sleep latency, wake after sleep onset, number of awakenings, sleep efficiency) and circadian activity rhythm assessment (mesor, amplitude, acrophase, etc.). Regulatory status: approved (FDA)

9.5 Describe the source records that will be used to collect data about subjects. (Attach all surveys, scripts, and data collection forms.)

- **Demographics and Treatment Survey:** A general demographics questionnaire used to assess personal (age, gender), lifestyle (smoking history and current use of tobacco, stimulants, and alcohol), disease (stage and type of lung cancer) and treatment (schedule, type and dose of chemotherapy, other medications used and side effects) factors.
- **Functional Assessment of Chronic Illness Therapy Fatigue (FACIT) (Cella, Lai et al. 2011)** – The FACIT Measurement System is a part of a collection of quality of life questionnaires targeted to the management of chronic illness. FACIT has 13-items with a 5-point Likert scale with well established validity and reliability to assess fatigue.

- **Insomnia Severity Index (ISI) (Bastien et al., 2001)** – is a self-report psychometrically sound instrument used to measure perceived insomnia severity.
- **Sleep diary** – is a self-report instrument to prospectively assess an individual's sleep.
- **Functional Assessment of Cancer Therapy-Lung Scale (Butt, Z., et al., 2005)** FACT-L is a widely used quality of life instrument in lung cancer clinical trials and provides validated clinically meaningful score changes.
- **Epworth Sleepiness Scale (Johns 1991)** – is a self-reported questionnaire assessing trait daytime sleepiness that relies on retrospective reports of dozing behavior in various hypothetical situations to establish an assessment of a patient's global level of sleepiness.
- **Morningness-Eveningness Horne-Ostberg/Questionnaire (MEQ) (Horne and Ostberg 1976)** – is a self-reported questionnaire used to determine individual differences in morningness and eveningness—the degree to which respondents are active and alert at certain times of the day. Results of this questionnaire inform circadian typology.
- **Treatment Expectation (investigator developed) self-report survey to determine treatment expectations for treatment effectiveness before and after treatment.**
- **Pittsburgh Sleep Quality Index (Buysee et al., 1991)**, a 19-item, self-report questionnaire assesses sleep quality and quantity. The PSQI assesses a range of sleep disturbances including: insomnia, sleep apnea and limb movement disorders, as well as daytime consequences of sleep.
- **Snellen Visual Acuity chart** – Assess visual acuity before and after the interventions.
- **Brief Fatigue Inventory (Mendoza, 1999)** – BFI is a valid and reliable measure of clinically significant fatigue, assessing fatigue severity, and impact of fatigue on daily functioning.
- **Hospital Depression and Anxiety Scale (Zigmond & Snaith, 1983).** HADS is valid and reliable self-assessment of depression and anxiety for inpatients and outpatients.

9.6 What data will be collected including long-term follow-up.

Response: Quantitative data on demographics, disease and treatment; screening for sleep apnea; self-report data on sleep, fatigue and quality of life; movement data used for objective sleep-wake data; treatment adherence and treatment expectations.

9.7 For HUD uses provide a description of the device, a summary of how you propose to use the device, including a description of any

screening procedures, the HUD procedure, and any patient follow-up visits, tests or procedures.

N/A

10.0 Data and Specimen Banking

10.1 If data or specimens will be banked for future use, describe where the data/specimens will be stored, how long they will be stored, how the data/specimens will be accessed, and who will have access to the data/specimens.

N/A

10.2 List the data to be stored or associated with each specimen.

N/A

10.3 Describe the procedures to release data or specimens, including: the process to request a release, approvals required for release, who can obtain data or specimens, and the data to be provided with specimens.

Response: N/A

11.0 Data Management

11.1 Describe the data analysis plan, including any statistical procedures.

Hypothesis testing will be conducted using 2x2 ANOVAs for the first specific aim, with Logistic Regressions for the second specific aim (predicting treatment response and non-response) and with Linear and Logistic Regressions for the third specific aim (predicting illness severity and treatment response).

11.2 Provide a power analysis.

Response:

The primary outcome for sleep is the sleep efficiency score. Previous research has indicated that persons with satisfactory sleep have a sleep efficiency score exceeding 85, whereas persons reporting unsatisfactory sleep have a score at most 70, with both groups reporting a standard deviation of approximately 15. The estimated effect size from this study

is 1. The goal of this study is to improve sleep efficiency from an unsatisfactory level to a satisfactory level. Using a large effect size of .08 with a one-tailed significance of .025 and power of 80%, the required sample size for the two-group comparison is 26 per group for a total sample of 52.

11.3 Describe the steps that will be taken to secure the data (e.g., training, authorization of access, password protection, encryption, physical controls, certificates of confidentiality, and separation of identifiers and data) during storage, use, and transmission.

All members of the research team have completed CITI training on ways to protect subject's data throughout the research process. Following informed consent, each participant will be assigned a unique numeric identifier. Consents will be stored in a locked file cabinet in a locked office in the School of Nursing. Data will be de-identified before being coded, entered, stored securely, backed up regularly, and analyzed using the SPSS software at the University at Buffalo School of Nursing in room 301B Wende Hall, [name]. To ensure safety in data management and data analysis, data entry will be performed on a protected computer, secured by the University at Buffalo Standards for Securing Regulated Private Data and the New York State Information Security Breach Notification Act with access limited by UBIT safety policies to data management, including: secure server and computer, base encryption, UBIT password and name account verification and daily electronic secure back up. Data destruction will be manually performed in accordance with the applicable institutional schedule at the end of its life cycle.

11.4 Describe any procedures that will be used for quality control of collected data.

All data is initially checked by the PI for completeness and incomplete data is reviewed with participant to ensure incomplete answers were addressed. All data that is coded and entered will be independently verified by at least one other research team member, with monthly random checks performed by the PI. Data analysis will begin with an assessment of means, standard deviations, frequencies and confidence intervals to identify any outliers. Outlier data will be reviewed with statistician on data management.

11.5 Describe how data and specimens will be handled study-wide:

Response: Data will be de-identified by assigning a unique subject number to each consented participant's data file. De-identified data will be abstracted from the electronic medical record and recorded on the Demographics and Treatment Survey after each eligible participant is

consented. De-identified data will be transferred to an SPSS file and stored on a password protected computer in a locked office in Wende Hall at the University at Buffalo School of Nursing within 24 hours. Demographics and Treatment Survey data will be stored in a locked file cabinet in room 301B Wende Hall. The PI, Research Assistant and co-investigators will have will have access to the SPSS de-identified data files.

11.6 What information will be included in that data or associated with the specimens?

Response: Demographics, lifestyle data, lung cancer treatment history, current medications, sleep, fatigue and quality of life survey results, sleep apnea and oxygen saturation data and circadian activity rhythm data.

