1.1 Hypothesis

Hypothesis 1: Subjects in the Bright Light Treatment group will exhibit significant improvements as compared to Dim Light Treatment in fatigue, sleep and circadian activity rhythms.

Hypothesis 2: Subjects typed during baseline as having circadian dysrhythmia using actigraphy (circadian phase and amplitude abnormalities) will be significantly more likely to exhibit treatment responses.

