be recruited over 2 years. Not all lung cancer survivors have sleep continuity disturbance, but in our current sleep study, we were able to recruit 20 lung cancer survivors with insomnia within 6 months at Roswell Park Cancer Institute. Retention rate of study participants is anticipated to be 80% based on our previous experience. Oversampling will result in the desired target sample size at this rate. At the time of enrollment in the study, three forms of contact information will be obtained, email address, telephone number, and address for delivery of the data collection instruments and return mailers. In addition, an alternate contact person will be obtained to help decrease loss to follow up due to the length of the study.

20.3 Describe the time that you will devote to conducting and completing the research.

Response: 20% of the PI's research time, 10% of the Co-I's time and the RA will work 10 hours/week on this study.

20.4 Describe your facilities.

Response: Recruitment Site: Roswell Park Cancer Institute (RPCI) was founded in 1898 is America's first cancer center and holds the National Cancer Institute designation of "comprehensive cancer center." RPCI has 133 hospital beds and 12 multidisciplinary clinics and is the only comprehensive cancer center of Western New York area. As a member of the prestigious National Comprehensive Cancer Network, RPCI has played a vital part in setting clinical guidelines for the care of Oncology patients. RPCI plays a pivotal part in cancer research with several ongoing funded research projects.

The thoracic clinic provides state of the art comprehensive multidisciplinary care to approximately 700 patients with lung cancer annually. The presence of several specialties -pulmonary medicine, medical oncology and thoracic surgery along with the undiagnosed clinic in a single location with additional support from nearby radiation oncology clinics and interventional radiation ensures excellent patient care and satisfaction. The patients with lung masses and suspected lung cancer are promptly seen by the pulmonary clinic or the undiagnosed clinic and scheduled for diagnostic biopsy procedures. Several multidisciplinary meetings are conducted each week to make complicated management decisions for the patients.

The VA WNYHS provides care to approximately 100 newly diagnosed veterans with lung cancer annually.

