23.0 Local Number of Subjects

23.1 Indicate the total number of subjects to be accrued locally.

Response: 50

23.2 If applicable, distinguish between the number of subjects who are expected to be enrolled and screened, and the number of subjects needed to complete the research procedures (i.e., numbers of subjects excluding screen failures.)

Response: 50 recruited and 40 to complete. We anticipate approximately 80% retention from previous research on this patient population.

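### Aim 1's pre-post 2x2 ANOVAs are valid but usually less precise than ANCOVA on the baseline already collected (26 per arm, d = 0.8, equal SDs: 67 / 81 / 95% versus 83 / 90 / 97% power at pre-post correlation 0.3 / 0.5 / 0.7)

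*Combined protocol and SAP*

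**What the plan says.** Hypothesis 1 (section 1.1) is that the bright-light arm "will exhibit significant improvements as compared to Dim Light Treatment in fatigue, sleep and circadian activity rhythms". Section 9.1 describes the design: "This pilot study will include 52 lung cancer survivors using a 2X2 mixed model with Pre-Post assessments in two groups". Section 9.2 places the measurements: "Surveys and actigraphy will be performed at baseline and again after treatment ends".

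The whole analysis text for this aim is the sentence in section 11.1: "Hypothesis testing will be conducted using 2x2 ANOVAs for the first specific aim". It does not say which term of the ANOVA tests the hypothesis, and it names no covariate.

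The power analysis in section 11.2 concerns sleep efficiency. It compares satisfactory and unsatisfactory sleepers, "with both groups reporting a standard deviation of approximately 15", and concludes that "the required sample size for the two-group comparison is 26 per group for a total sample of 52". It mentions neither a repeated measurement nor a pre-post correlation.

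**The concern.** A 2x2 pre-post ANOVA yields two main effects and an interaction. Only the interaction compares improvement between arms, and with two time points it is identical to a two-sample t test on change scores. A change score fixes the baseline coefficient at 1. ANCOVA estimates that coefficient, so it removes at least as much baseline variation apart from a small cost of estimation.

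Two things follow:

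- The plan may give up precision that its own baseline data would supply at almost no cost, in a trial of at most 26 per arm.
- The 80% power in section 11.2 is for an unadjusted comparison of one score, which is not the test in section 11.1. The two powers agree only under particular values of the pre-post correlation and the SDs, and the plan does not state those values.

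**Working it through.** **Inputs from the documents.** 26 per arm, one-tailed alpha .025, 80% power, SD about 15, all from section 11.2. That section first derives an effect size of (85 − 70)/15 = 1 and then prints .08 as the value used.

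**Inputs assumed.** Pre-post correlation r = 0.3, 0.5 or 0.7, and k = baseline SD / post SD = 1, 0.8 or 1.25. The effect d is in units of the post-treatment SD.

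**1. The plan's own figure.** For a two-sample t test the noncentrality is d√(n/2) with 2n − 2 df. With d = 0.8 and n = 26 this is 0.8 × √13 = 2.88 on 50 df, and power is 80.7%. With 25 per arm it is 79.1%, so 26 is reproduced. Taken literally, .08 would need 2,454 per arm, and d = 1 would need 17. The printed value is therefore read as 0.8.

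**2. Arm-by-time interaction.** The change-score variance is SD² × (1 + k² − 2rk), so the effective effect is d/√(1 + k² − 2rk), on 50 df. With k = 1:

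- r = 0.3: 0.8/√1.4 = 0.676, power 66.7%
- r = 0.5: 0.8/√1.0 = 0.800, power 80.7%
- r = 0.7: 0.8/√0.6 = 1.033, power 95.5%

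With equal SDs, the interaction reaches 80% only from r = 0.49 upwards.

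**3. ANCOVA.** The residual variance is SD² × (1 − r²), so the effective effect is d/√(1 − r²), on 2n − 3 = 49 df. Averaging over chance baseline imbalance multiplies the variance by 1 + 1/(2n − 4) = 1 + 1/48 = 1.021 on average. The result does not depend on k.

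- r = 0.3: 0.8/√0.91 = 0.839, power 83.5%
- r = 0.5: 0.8/√0.75 = 0.924, power 89.8%
- r = 0.7: 0.8/√0.51 = 1.120, power 97.5%

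**4. Power over the assumed range** (one-sided .025):

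| Setting | Test | r = 0.3 | r = 0.5 | r = 0.7 |
|---|---|---|---|---|
| n = 26, d = 0.8 | ANCOVA, any k | 83.5% | 89.8% | 97.5% |
| n = 26, d = 0.8 | Interaction, k = 1 | 66.7% | 80.7% | 95.5% |
| n = 26, d = 0.8 | Interaction, k = 0.8 | 74.7% | 87.0% | 97.5% |
| n = 26, d = 0.8 | Interaction, k = 1.25 | 55.6% | 69.5% | 88.1% |
| n = 26, d = 1 | ANCOVA | 95.6% | 98.1% | 99.8% |
| n = 26, d = 1 | Interaction, k = 1 | 84.8% | 94.2% | 99.5% |
| n = 20, d = 0.8 | ANCOVA | 72.2% | 80.1% | 92.5% |
| n = 20, d = 0.8 | Interaction, k = 1 | 54.9% | 69.3% | 88.9% |

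At n = 20 and d = 0.8 the unadjusted comparison has 69.3%. A simulation of 40,000 trials per cell (n = 26, d = 0.8, k = 1) gave 67.0 / 81.1 / 95.2% for the interaction and 83.7 / 90.1 / 97.4% for ANCOVA.

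**5. Precision in sleep-efficiency points.** The 95% CI half-width is t × 15 × √(variance factor) × √(2/26). With equal SDs and r = 0.3 / 0.5 / 0.7 it is 9.9 / 8.4 / 6.5 for the interaction and 8.1 / 7.3 / 6.0 for ANCOVA.

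**6. How far each choice can lose.** Since 1 + k² − 2rk = (1 − r²) + (k − r)², the change-score variance is never below ANCOVA's residual variance, and the two are equal when r = k. ANCOVA's only loss is therefore the estimation factor: at most 1/48 = 2.1% of variance at 26 per arm, or 1/36 = 2.8% at 20 per arm. In the other direction, at r = 0.3 and k = 1 the change-score variance is 1.4/(0.91 × 1.021) = 1.5 times ANCOVA's. At k = 0.8 the change score is the more precise for r between about 0.70 and 0.87, but power there differs by about 0.1 percentage point or less. At k = 1 it is the more precise only for r above 0.96.

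**The case against.** The strongest reply is that this is a choice between two valid methods in a self-described pilot. The pre-post ANOVA already uses the baseline through its time factor, and nothing in the documents contradicts it. That is correct, and it is why the point is one of precision only.

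The second reply is that any single power gap rests on assumed inputs. This also stands. At d = 1, the effect size that section 11.2 first derives, the gap at r = 0.5 with equal SDs is 94.2% versus 98.1%. At d = 0.8 with k = 0.8 and r = 0.5 it is 87.0% versus 89.8%, and at r = 0.7 it disappears. Recruiting people because they sleep badly (section 3.1) could shrink the baseline SD, which narrows the gap, but could also lower r, which widens it. The SD of about 15 in section 11.2 describes two kinds of sleeper, not two time points, so it makes equal SDs plausible without establishing them.

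Neither reply favours the change score. With r and k unknown, ANCOVA's possible loss is about 2% of variance, while the change score's possible loss is many times that. Nor do they answer the narrower point that 11.1 does not name its test term and 11.2 does not give that term's power.

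**Conclusion.** The concern holds. The planned interaction test is unbiased under randomisation and has the correct type I error, but it is usually less precise than ANCOVA on data the trial already collects. At 26 per arm, d = 0.8 and equal SDs, the difference in power is about 17 points at r = 0.3, 9 at r = 0.5 and 2 at r = 0.7. It is smaller if the baseline SD is below the post SD or if d = 1, and larger if the baseline SD exceeds the post SD.

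These sizes depend on assumed values of r and the SD ratio, and on reading the printed effect size as 0.8. The direction of the recommendation does not depend on them, because ANCOVA's worst-case loss is bounded at about 2.1% of variance. The change is worth making, but an analysis run as now written would not be invalid.

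**What to change.** **Section 11.1.** Replace the ANOVAs for aim 1 with wording such as:

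> For each outcome, the post-treatment value is compared between arms, as randomised, by ANCOVA with that outcome's baseline value as covariate; the adjusted mean difference with 95% CI is reported.

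**Section 11.2.** After confirming that the effect size is 0.8, write:

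> With 26 analysed per arm, an unadjusted comparison of one score has about 80% power (d = 0.8, one-sided .025). The planned ANCOVA has about 83 / 90 / 97% power if the pre-post correlation is 0.3 / 0.5 / 0.7 (assumed).

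**If the 2x2 ANOVA is kept.** Name the arm-by-time interaction as the test of Hypothesis 1, and give its power over the same correlations with the SD assumption stated.

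**Separately,** settle the number to be analysed, since every power statement depends on it. Sections 3.1 and 9.1 give 52. Section 20.2 speaks of fifty recruits and says "Oversampling will result in the desired target sample size at this rate". Section 23.2 gives "50 recruited and 40 to complete".

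**Cost.** Two or three sentences and one degree of freedom. No new data are needed, because baseline values are already collected (section 9.2), and the planned software, SPSS (section 11.3), fits the model.

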13.0 Withdrawal of Subjects

13.1 Describe anticipated circumstances under which subjects will be withdrawn from the research without their consent.

Subjects will be withdrawn from the research without their consent if they are unable to complete their responsibilities listed on the consent form or if they falsify responses.

13.2 Describe any procedures for orderly termination.

The participants that require early termination from the study will receive a telephone call alerting them to the termination and thanking them for their participation. If participants are not available via telephone, a letter notifying them of their termination will be mailed to their home address.

13.3 Describe procedures that will be followed when subjects withdraw from the research, including partial withdrawal from procedures with continued data collection.

Response: It is conceivable that some participants may decide not to fully participate, for example, not wear the light therapy (i.e. Re-Timers), but complete survey and actigraph data. Their data is still valuable. Data collection would continue and participants would receive appropriate compensation.

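### Aim 1's pre-post ANOVA compares change scores among people with both scores; adjusting for baseline would be more precise and would remove bias from baseline-related loss

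*Combined protocol and SAP*

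**What the plan says.** Section 11.1 gives the Aim 1 analysis in one clause: "Hypothesis testing will be conducted using 2x2 ANOVAs for the first specific aim". Section 9.1 supplies the structure, a "2X2 mixed model with Pre-Post assessments in two groups", so the two factors are arm and time, with one assessment before treatment and one after.

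The sample size in section 11.2 concerns sleep efficiency, with "both groups reporting a standard deviation of approximately 15". It continues "Using a large effect size of .08" "with a one-tailed significance of .025 and power of 80" per cent, and concludes that "the required sample size for the two-group comparison is 26 per group for a total sample of 52".

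On losses, section 20.2 states "Retention rate of study participants is anticipated to be 80% based on our previous experience", and section 23.2 translates this into 50 recruited and 40 completing. Section 13.3 covers people who do not wear the light but still give survey and actigraph data: "Data collection would continue and participants would receive appropriate compensation". Section 11.4 has incomplete answers reviewed with the participant. The document names no analysis set, no method for a missing post-treatment score and no sensitivity analysis.

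**The concern.** A standard 2x2 mixed ANOVA needs both scores from each person, so anyone without a post score drops out. What remains is a comparison of change scores in a subset whose make-up may depend on the arm.

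A change score carries the full baseline value with a coefficient of minus one. If the people who stay in one arm had better baseline sleep than those who stay in the other, regression to the mean alone makes their changes differ. That difference is then read as an effect of light. Adjusting for baseline removes this component, and the named ANOVA does not. At stake are the size of the estimated light effect and, even when loss is harmless, its precision in a small trial.

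**Working it through.** **Inputs from the document.** SD 15; 26 per arm; one-sided 0.025; 80% power (all section 11.2). Retention 80% (sections 20.2 and 23.2).

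**Assumed inputs.** All 20% lost after randomisation, equally in both arms; pre-post correlation r of 0.3, 0.5 or 0.7; where loss is not random, log-odds of leaving of 1 per baseline SD; bivariate normal scores.

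**Step 1: the plan's own sample size.** A two-sample t calculation at d = 0.8, one-sided 0.025 and 80% power gives 25.5, so 26 per arm, as stated. The printed .08 would need 2,453 per arm, and the effect size of 1 also mentioned in 11.2 would need 17. I therefore read .08 as 0.8, which makes the effect 0.8 x 15 = 12 points. The document does not state 12 points.

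**Step 2: what the ANOVA estimates.** With two time points, the arm-by-time F test is the t-test on change (post minus pre). Let s be the amount by which the mean baseline of those who stay exceeds that of everyone randomised to the arm. If loss depends on baseline only, then

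bias = -(1 - r) x (s in bright arm - s in dim arm).

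**Step 3: simulation.** 6,000 trials per scenario, 26 per arm, true effect 12, r = 0.5:

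| Who leaves, bright arm / dim arm | Change-score estimate |
|---|---|
| random / random | 12.0 |
| worse sleepers / random | 10.7 |
| better sleepers / random | 13.3 |
| worse sleepers / better sleepers | 9.4 |
| better sleepers / worse sleepers | 14.6 |

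The same baseline pattern in both arms gives about 12. The baseline-adjusted estimate is 11.9 to 12.1 in all these scenarios.

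**Step 4: check against the formula.** The shift from 12 to 9.4 is 2.6 points, or 1.3 per arm. Dividing by 1 - 0.5 gives s = 2.6 points, about 0.17 SD, in opposite directions in the two arms. Carrying s = 2.6 to other correlations:

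- r = 0.3: 0.7 x 2.6 x 2 = 3.6, so 8.4 to 15.6 (simulated: about 8.4 to 15.6).
- r = 0.7: 0.3 x 2.6 x 2 = 1.6, so 10.4 to 13.6 (simulated: 10.5 to 13.6).

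**Step 5: precision under random loss.** About 26 x 0.8 = 20.8 per arm have both scores.

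- Change score at r = 0.5: variance 2(1 - r) x 225 = 225; SE = sqrt(225 x 2/20.8) = 4.65 (simulated about 4.7).
- Baseline-adjusted: variance (1 - r squared) x 225 = 168.75; SE = sqrt(168.75 x 2/20.8) = 4.03 (simulated about 4.1, because the slope is estimated).

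The variance ratio is (1 + r)/2 = 0.75. For comparison, a change-score analysis with no losses has SE sqrt(225 x 2/26) = 4.16, so at this correlation baseline adjustment roughly recovers the precision lost with one participant in five.

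**Step 6: loss that baseline does not explain.** Suppose the 20% who leave the bright arm gained nothing over dim light. The as-randomised effect is 0.8 x 12 + 0.2 x 0 = 9.6. Completers show 12, an overstatement of 12/9.6 = 1.25. Baseline adjustment also returns about 12 here, so it does not help.

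**The case against.** Several points on the other side stand.

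- A reader might infer that any difference between arms in who leaves biases the result. It does not. If leavers are typical of their arm, 30% loss against 10% gives no bias. The same loss and the same kind of leaver in both arms gives none either when there is no true effect. Unequal loss alone costs only precision.
- A reader might infer that one in five randomised participants will be lost. The 80% is counted from recruitment. Section 3.2 randomises only after the pretreatment measures, whereas section 22.1 says only that it follows consent. Some of the loss may therefore come earlier and leave the arm comparison untouched. Section 12.4 describes one week of treatment and two weeks of later data collection. Section 20.2 also expects oversampling to reach the target, though it gives no number.
- A reader might infer that people who do not wear the light are excluded. Nothing says so. Section 13.3 keeps their data, and no per-protocol set is defined. Analysis as randomised is an unstated default, which 11.1 should state.
- Section 9.1 speaks of a mixed model, which could mean a likelihood-based one. Section 11.1 says ANOVA, so dropping incomplete pairs follows from the standard form of the named method and is not something the document states.
- With one pre and one post score, a likelihood repeated-measures model gives essentially the same answer as ANCOVA in completers. It is no remedy for loss that depends on the unseen outcome.

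The trial is a pilot, and nothing in the document suggests the particular loss patterns simulated. But the pilot plans formal hypothesis tests, and the gain in precision does not depend on those patterns.

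**Conclusion.** The point holds as a weakness of the named method. The 2x2 ANOVA is a completers' change-score comparison, open to bias if loss after randomisation relates to baseline differently by arm, and less precise than baseline adjustment even when loss is random.

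Under the stated assumptions the 12-point effect could appear as anything from 9.4 to 14.6 at r = 0.5, with a wider range at r = 0.3 and a narrower one at r = 0.7. The extremes need opposite loss patterns in the two arms; a pattern in one arm only moves the estimate by about 1.3 points. All these figures shrink if part of the 20% is lost before randomisation. They show what could happen and do not forecast it. The precision gain (SE about 4.7 to 4.1) also depends on r, and diminishes as r rises.

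**What to change.** In section 11.1:

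1. Replace the 2x2 ANOVA for Aim 1 with an ANCOVA of the post score on arm and baseline, or the near-equivalent likelihood repeated-measures model with a common baseline mean and arm-specific post means.
2. State that all randomised participants are analysed in their assigned arm, including the non-wearers whose data section 13.3 keeps.
3. Add one sensitivity analysis that gives bright-arm participants without a post score the dim-arm mean. This addresses outcome-related loss, which the first step cannot; in the example of step 6 it would return 9.6.
4. Report losses by arm, split into before and after randomisation, with reasons.

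The cost is a few sentences in the plan and a small amount of extra analysis on data already collected. No added participants or visits are needed.
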